## **13.1.3 Efficacy Analysis**

The primary efficacy variable will be the percentage of days without daytime or night time heartburn over 4 weeks as assessed by daily eDiary. Comparisons between dexlansoprazole capsules and placebo will be made using a Wilcoxon rank-sum test.

The secondary efficacy variable will be the percentage of days without nighttime heartburn over 4 weeks as assessed by daily eDiary. Comparisons between dexlansoprazole capsules and placebo will be made using a Wilcoxon rank-sum test.

An additional efficacy variable will be the severity of GERD symptoms at Weeks 2 and 4 as assessed by the investigator. The severity of GERD symptoms at Weeks 2 and 4 will be analyzed using a Cochran-Mantel-Haenszel (CMH) test for ordered responses with baseline severity as the stratum. The percentage of days without rescue medication over 4 weeks as assessed by daily eDiary will be analyzed using Wilcoxon rank-sum test.

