5.6 Demographic and Other Baseline Characteristics

Demographic and baseline characteristics variables were summarized using the safety analysis set.

For continuous variables (age, weight, height, and body mass index [BMI]), summary statistics were generated.

For categorical variables, the number and percentage of subjects in each category was presented.

The following baseline characteristics were summarized.

- Number of days with daytime or nighttime heartburn between Study Days -8 and -2, inclusive.
- Number of days with nighttime heartburn between Study Days -8 and -2, inclusive.
- Number of days with daytime heartburn between Study Days -8 and -2, inclusive.
- Mean severity of daytime and nighttime heartburn between Study Days -8 and -2, inclusive.
- Mean severity of nighttime heartburn between Study Days -8 and -2, inclusive.
- Mean severity of daytime heartburn between Study Days -8 and -2, inclusive.
- Baseline severity of GERD symptoms as assessed by the investigator.
- Baseline number of days with daytime/nighttime rescue medication use.

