5.10.3 Additional Efficacy Endpoints

The severity of GERD symptoms at Weeks 2 and 4 was analyzed using a Cochran-Mantel-Haenszel (CMH) test for ordered responses with baseline severity as the stratum. The p value was presented for the difference between dexlansoprazole capsules and placebo; the difference was considered significant if the p-value was less than 0.05.

The percentage of days without rescue medication over 4 weeks as assessed by daily eDiary was analyzed using the Wilcoxon rank-sum test.

In addition, descriptive statistics were presented for the endpoints below:

- The percentage of days without daytime heartburn over the 4 weeks of treatment as assessed by daily eDiary.
- The severity of daytime and nighttime heartburn hurt over the 4 weeks of treatment as assessed by daily eDiary.
- The severity of nighttime heartburn hurt over the 4 weeks of treatment as assessed by daily eDiary.
- The severity of daytime heartburn hurt over the 4 weeks of treatment as assessed by daily eDiary.

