6.6.2 Concomitant Medications

Concomitant medications included any medication taken which was ongoing as of Study Day 1, ended on or after Study Day 1 or started on or after Study Day 1 and no more than 1 day after the last dose of study drug.

For the concomitant medications that started and stopped prior to baseline, the incidence was similar across the treatment groups, and the most common concomitant medications were propofol: dexlansoprazole capsules group (54.2%) and placebo group (54.6%); dyclonine hydrochloride: dexlansoprazole capsules group (43.0%) and placebo group (34.3%); and hydrotalcite: dexlansoprazole capsules group (29.0%) and placebo group (38.0%).

For the concomitant medications that started prior to and were ongoing at baseline, the incidence in dexlansoprazole capsules group (15.9%) was less than that in placebo group (27.8%), and the most common concomitant medications was hydrotalcite: dexlansoprazole capsules group (3.7%) and placebo group (8.3%).

For the concomitant medications that started after baseline, the incidence in dexlansoprazole capsules group (34.6%) was less than that in placebo group (45.4%), and the most common concomitant medications was hydrotalcite: dexlansoprazole capsules group (15.9%) and placebo group (23.1%).

For the concomitant medications that were ongoing at baseline and those that started after baseline, the incidence in dexlansoprazole capsules group (39.3%) was less than that in placebo group (53.7%), and the most common concomitant medications was hydrotalcite: dexlansoprazole capsules group (16.8%) and placebo group (25.9%).

The details of the concomitant medications information are summarized in Table 15.1.12.1, 15.1.12.2, 15.1.12.3, and 15.1.12.4, and by-subject listing are presented in Appendix 16.2.4.5. The glossary of medication history and concurrent medications by preferred medication name is provided in Table 15.1.13.

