9.2 Conclusion

In this 4-week study of dexlansoprazole 30 mg or placebo in Chinese subjects with symptomatic nonerosive GERD, dexlansoprazole was safe and well tolerated. Subjects taking dexlansoprazole had a greater percentage of days without daytime or nighttime heartburn (difference of 19 percentage points) and without nighttime heartburn alone (difference of 13 percentage points) than subjects taking placebo, but the differences between the treatment groups were not statistically significant. Statistically significant improvements were observed, however, in several investigator-assessed GERD symptoms after 4 weeks of treatment with dexlansoprazole (an additional endpoint). In addition, subjects taking dexlansoprazole used statistically significantly less rescue medication than those taking placebo.

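### The rescue-medication result (P=0.009) comes from a test with no baseline term, although more placebo subjects took hydrotalcite before treatment, so it may partly reflect a pre-treatment difference

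*SAP*

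**What the plan says.** Protocol 13.1.3 sets the test for rescue-free days: the endpoint "will be analyzed using Wilcoxon rank-sum test". SAP 5.10.3 repeats it: "The percentage of days without rescue medication over 4 weeks as assessed by daily eDiary was analyzed using the Wilcoxon rank-sum test". Neither names a covariate or stratum. In the same SAP section, investigator-assessed severity is analysed with a "Cochran-Mantel-Haenszel (CMH) test for ordered responses with baseline severity as the stratum". So one additional endpoint is adjusted for its baseline and its neighbour is not.

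A baseline value exists. Under Protocol 6.1 and 9.1.7, subjects record rescue use in the eDiary throughout screening, and SAP 5.6 lists "Baseline number of days with daytime/nighttime rescue medication use" among the baseline characteristics. The results text in 6.4 comments only on heartburn days and heartburn severity, and refers to Table 15.1.8 for the rest. That table is not in the documents supplied.

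Protocol 8.1.1.2 names hydrotalcite (Talcid) and Gaviscon as rescue medicines. For medicines that began and ended before baseline, SAP 6.6.2 gives "hydrotalcite: dexlansoprazole capsules group (29.0%) and placebo group (38.0" (both figures are percentages). For hydrotalcite still ongoing at baseline it gives 3.7% and 8.3%.

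Section 7.2.2 reports P=0.009 for rescue-free days. The conclusion in 9.2 says that "subjects taking dexlansoprazole used statistically significantly less rescue medication than those taking placebo". The synopsis and 9.1 say much the same, while 7.3 puts it in terms of days.

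**The concern.** Subjects who took antacid during screening are likely to take it again during treatment. If the placebo arm started with more such subjects, an unadjusted comparison may credit the drug with part of a difference that was already there.

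The primary (P=0.057) and secondary (P=0.268) endpoints were not significant. Rescue use is therefore one of the two positive efficacy statements in the conclusion, the other being investigator-assessed symptoms. A reader of 7.2.2 or 9.2 is not told that the arms differed in hydrotalcite use before the first dose.

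**Working it through.** **Inputs.** Arm sizes are 108 placebo and 107 dexlansoprazole (6.3). Hydrotalcite percentages are from 6.6.2. Mean rescue-free days are 94.40% vs 97.81%, and subjects with 100% rescue-free days are 69 vs 84 (7.2.2). Figures below are placebo vs dexlansoprazole.

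**1. Counts.** The percentages map to whole subjects. Chi-square p uses z = (p1 − p2)/√[p(1 − p)(1/n1 + 1/n2)]. For the first row, z = 0.0899/√[0.3349 × 0.6651 × (1/108 + 1/107)] = 1.40, so p = 0.16.

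| Use | Counts | Gap (points) | Odds ratio | p |
|---|---|---|---|---|
| Hydrotalcite, stopped before baseline | 41 vs 31 | 9.0 | 1.50 | 0.16 |
| Hydrotalcite, ongoing at baseline | 9 vs 4 | 4.6 | 2.34 | 0.16 |
| Hydrotalcite, ongoing at or started after baseline | 28 vs 18 | 9.1 | 1.73 | 0.10 |
| eDiary, any rescue day on treatment | 39 vs 23 | 14.6 | 2.06 | 0.018 |

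The second odds ratio is (9 × 103)/(4 × 99) = 2.34. The last row is 108 − 69 = 39 and 107 − 84 = 23.

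**2. The reported figure.** The exact Wilcoxon p needs subject-level data. An approximation used the 39 and 23 users, with non-zero rescue percentages drawn from an exponential shape (assumption) and scaled to the stated arm means of 5.60% and 2.19% of days. It gives a median p of 0.010 (5th to 95th percentile 0.007 to 0.016). This is consistent with P=0.009 but is not a reproduction.

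**3. How many prior users?** The overlap between the stopped and ongoing groups is not reported. Any prior use is therefore 41 to 50 on placebo (41 + 9) and 31 to 35 on dexlansoprazole (31 + 4). Subjects can appear in more than one category: 9 + 25 − 28 = 6 placebo and 4 + 17 − 18 = 3 dexlansoprazole subjects were both ongoing at baseline and recorded as starting after it. Zero overlap is thus a bound, not a best guess.

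**4. Stratified test.** The within-arm odds ratio (OR) linking prior to on-treatment use is not in the documents, so it was varied from 1 to 1000. In an arm of n subjects with a prior and b on-treatment users, the number x in both solves x(n − a − b + x) = OR(a − x)(b − x). For OR = 8 with 41 vs 31 prior users, x = 26.5 of the 39 placebo users and 15.0 of the 23 dexlansoprazole users. A van Elteren test (rank sums within prior-use strata, weight 1/(N + 1)) was then run on the simulated rescue days. Median p:

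| Assumed OR | 41 vs 31 | 50 vs 35 (no overlap) | 50 vs 31 (extreme) |
|---|---|---|---|
| 1 | 0.011 | 0.012 | 0.012 |
| 4 | 0.023 | 0.035 | 0.059 |
| 8 | 0.026 | 0.053 | 0.100 |
| 16 | 0.025 | 0.061 | 0.139 |
| 50 | 0.018 | 0.069 | 0.188 |
| 1000 | 0.012 | 0.071 | 0.225 |

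These are medians. In the 41 vs 31 column the 95th percentile across simulations reaches 0.064. The 50 vs 31 column needs no overlap on placebo and complete overlap on dexlansoprazole. The pattern 41 vs 35 was not run; its baseline gap is smaller (38.0% vs 32.7%, p = 0.42).

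**5. Direction.** In a Cochran-Mantel-Haenszel analysis of any vs no rescue use with OR 3 to 20, the adjusted odds ratio is 1.93 to 2.09 (41 vs 31) or 1.73 to 1.84 (50 vs 35), against 2.06 unadjusted. The lowest value in any scenario is 1.25 (50 vs 31, OR 1000). It never falls below 1.

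**The case against.** The rank-sum test was pre-specified in the protocol, and under randomisation it controls type I error without baseline adjustment. That stands: the issue is how to read the result given the observed imbalance, not whether the test is valid.

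Each reported hydrotalcite gap is compatible with chance (p about 0.16). That is true, but the influence of a prognostic baseline variable does not depend on its own p-value.

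Hydrotalcite is a proxy. The counts come from medication records, omit Gaviscon, and count subjects rather than days. On treatment they find 28 and 18 users where the eDiary finds 39 and 23. Whether eDiary rescue days were imbalanced is not visible in the documents. This stands, and it is a reason to use the eDiary baseline.

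A reader might infer more than the documents support:

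- *That the gap did not widen on treatment.* Hydrotalcite started after baseline differs by 7.2 points (23.1% vs 15.9%), less than the 9.0 points before baseline. But that row omits subjects continuing from baseline. The fuller figure is 9.1 points with a higher odds ratio (1.73 vs 1.50), and the endpoint's own source, the eDiary, shows 14.6 points.
- *That adjustment removes significance.* The yes/no analysis gives p of 0.037 to 0.056 (41 vs 31) or 0.056 to 0.146 (50 vs 35) for OR 3 to 20. But it starts at 0.018 and discards the number of days, so it overstates the fragility of the planned test.
- *That the adjusted result should replace the planned one.* The covariate would be chosen after both the imbalance and the outcome were known.

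**Conclusion.** The concern holds in a limited form. P=0.009 may partly reflect more antacid use on placebo before treatment, and the report neither adjusts for this nor mentions it beside the result. With stratification on prior use, median p is about 0.011 to 0.026 with 41 vs 31 prior users and 0.012 to 0.071 with 50 vs 35. It reaches about 0.23 only in the extreme overlap pattern. These ranges rest on an assumed prior-to-later association, an assumed overlap and an assumed shape for rescue days. The direction favours dexlansoprazole throughout, so the documents do not show that imbalance explains the effect. Only the sponsor's eDiary data can settle whether significance survives.

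The primary result is untouched. The raw difference is 97.81 − 94.40 = 3.41 points, about 1 day in 28 (0.0341 × 28 = 0.95).

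One wording point holds regardless. The eDiary (Protocol Appendix G) asks only whether rescue was taken, so a claim of less rescue medication goes beyond the data.

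**What to change.** - Keep the pre-specified Wilcoxon result as it is.
- Report baseline eDiary rescue days by arm beside it in 7.2.2.
- Add an analysis of rescue-free days adjusted for baseline rescue days, labelled post hoc: a van Elteren test stratified by any vs no baseline rescue, or rank ANCOVA. State the baseline window first. Section 5.6 gives Study Days -8 to -2 for heartburn but no window for rescue.
- In the synopsis, 7.3, 9.1 and 9.2, qualify the rescue statement with the adjusted result and the pre-treatment difference.
- Where the synopsis, 9.1 and 9.2 speak of less rescue medication, write *fewer days with rescue use*. Section 7.3 already speaks of days.

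The cost is one re-run on data already collected and a few sentences. The downside is that the adjusted p-value may be less favourable.

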5.11 Pharmacokinetic/Pharmacodynamic Analysis

Not applicable.

5.12 Other Outcomes

Not applicable.

5.13 Safety Analysis

All safety analyses were performed using the safety analysis set.

5.13.1 Adverse Events

All AEs were coded using the Medical Dictionary for Regulatory Activities (MedDRA).

A treatment-emergent adverse event (TEAE) was defined as an AE that started or worsened on or after Study Day 1 (defined as day first dosed), and no more than 30 days after the last dose of study drug. All TEAEs were listed by subject number and MedDRA coding. A listing of all unique coded terms was also provided.

The number and percentage of subjects with treatment-emergent AEs was summarized in several different tables:

- All AEs by system organ class (SOC), high level term (HLT), and preferred term (PT).
- Treatment-related AEs by SOC, HLT, and PT.
- Most frequent AEs by SOC and PT (sorted by total frequency of PT occurring in $\geq 5\%$ of subjects in any treatment group).
- Most frequent treatment-related AEs (TRAEs) by HLT and PT (sorted by total frequency of HLT occurring in $\geq 2\%$ of subjects in any treatment group). If no events met the 2% criteria, the most frequent TRAEs were defined as those events occurring in 2 or more subjects.
- Severity of all AEs by SOC and PT (mild, moderate, or severe).
- Severity of TRAEs by SOC and PT (mild, moderate, or severe).
- Relationship to study drug for all AEs by SOC and PT (not related, related).

A subject with 2 or more AEs within the same level of the MedDRA term was counted only once in that level using the most extreme incident (most severe for the severity tables and related for the relationship to study drug tables).

Additionally, treatment-emergent serious adverse events, deaths, and TEAEs resulting in premature discontinuation from study drug were listed and summarized by SOC, HLT and PT. The most frequent treatment-emergent non-serious AEs were also summarized by SOC, HLT and PT.

A pretreatment event was defined as an AE that ends prior to Study Day 1 (defined as day first dosed), or ends but not worsens on or after Study Day 1 (defined as day first dosed). A list of

pretreatment AEs by subject number and MedDRA coding was presented separately. Pretreatment AEs were summarized by SOC and PT.

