# **10.0 PRETREATMENT EVENTS AND ADVERSE EVENTS**

### 10.1 Definitions

#### **10.1.1 Pretreatment Events**

A pretreatment event (PTE) is defined as any untoward medical occurrence in a clinical investigation subject who has signed informed consent to participate in a study but prior to administration of any study medication; it does not necessarily have to have a causal relationship with study participation.

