5.2.3 Handling of Missing/Partial Date

Completely missing start or end dates remained missing, with no imputation applied.

Partial dates were imputed using the below conventions:

- If the partial date was a start date and:
 - If only missing day, then impute as the first day of the month.
 - If missing both month and day then, impute as the first day of the year.
- If the partial date was an end date and:
 - If only missing day, then impute as the last day of the month.
 - If missing both month and day, impute as the last day of the year.

- If the partial date was in the same month (only missing day) or same year (missing both month and day) as the study treatment, and the imputed start date of an adverse event (not pretreatment event) was prior to the start of study treatment, then the start date of study treatment was assumed to be the start date. The AE would then be considered as start on treatment (worst case scenario).
- If the imputed end date was after the subject’s last visit date (or last contact date), then the last visit date (or last contact date), was considered as the end date.

The recorded partial date was displayed in the listings.

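### SAP 5.13.1 defines a pretreatment event with no onset condition, so the pretreatment listing and summary misclassify events; an effect on the TEAE count is possible only for partial start dates and is not shown

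*SAP*

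**What the plan says.** SAP 5.13.1 gives two ways for an AE to be a pretreatment event. Either it is over before Study Day 1, "or ends but not worsens on or after Study Day 1". There is no start-date condition in either limb. The same section defines a TEAE as "an AE that started or worsened on or after Study Day 1", up to 30 days after the last dose, and does not exclude pretreatment events from that class. Pretreatment events are listed separately and summarised by SOC and PT.

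SAP 5.2.3 handles partial start dates. When only the day is missing, the rule is "If only missing day, then impute as the first day of the month". A worst-case step then moves the start to the first-dose date if the partial date lies in the month (or year) of treatment and "the imputed start date of an adverse event (not pretreatment event) was prior to the start of study treatment".

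Protocol 10.1.1 defines a pretreatment event by timing of occurrence, in a subject "who has signed informed consent to participate in a study but prior to administration of any study medication". Protocol 10.2.1.1 agrees: collection of pretreatment events stops at first dose, and AE collection starts there.

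**The concern.** The protocol's criterion is onset. The SAP's criterion is the end date plus absence of worsening, and the SAP neither repeats nor cites the protocol's rule. The two can disagree on the same event.

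The direct consequence is a wrong pretreatment listing and SOC/PT summary. There is also a possible indirect one. The worst-case step in SAP 5.2.3 is withheld from pretreatment events, and 5.13.1 contains the SAP's only definition of that term. If the two sections are read together, the definition decides which partially dated events are moved to the first-dose date, and so could touch TEAE incidence, a headline safety result.

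**Working it through.** **Inputs.** The two limbs and the TEAE definition come from SAP 5.13.1, and the partial-date rules from SAP 5.2.3. The onset rule comes from protocol 10.1.1 and 10.2.1.1. TEAE counts are in SAP Table 8.a, and the safety-set sizes (108 placebo, 107 dexlansoprazole) are in SAP 6.3.

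**Reported figures reproduced.** 35/108 = 32.4% and 39/107 = 36.4%. The severity rows add up: 27 + 6 + 2 = 35 and 26 + 10 + 3 = 39. Events: 70 + 63 = 133.

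**Classification check.** Put first dose on the 15th of a month. Vary the true start (10th or 20th), the end (12th, 25th or ongoing), worsening (yes or no) and whether the start day is recorded. An ongoing event has no end date, and a worsened event is treated as a TEAE only. Impossible combinations, and worsening in an event that ended before first dose, are left out. That leaves 18 patterns. Each was classified under the SAP text, with 5.2.3 read through 5.13.1, and then under the protocol's onset rule. Four differ:

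| Event | SAP as written | Onset rule |
|---|---|---|
| A. Starts 20th, resolves 25th, no worsening, full dates | Pretreatment and TEAE | TEAE |
| B. Starts 10th, ongoing, unchanged, full dates | Neither | Pretreatment |
| C. As A, start day missing | Pretreatment, not TEAE | TEAE |
| D. As B, start day missing | TEAE, not pretreatment | Pretreatment |

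- **A:** the second limb is met, and so is the TEAE definition. The event is listed twice, but the TEAE count is right.
- **B:** with no end date, neither limb is met. It is not a TEAE, which is correct, but it drops out of the pretreatment outputs.
- **C:** the start is imputed to the 1st. The second limb makes the event pretreatment, so the worst-case step does not apply and the start stays before first dose. A TEAE is lost.
- **D:** with no end date the event is not pretreatment, so the imputed start is moved from the 1st to the 15th. A TEAE is added.

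The TEAE result therefore changes only in C and D, which err in opposite directions. Both need a partial start date.

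**Scale.** The number of partial AE start dates is not given, so the following is an assumption for scale only. One subject is 1/108 or 1/107, about 0.9 points. If k subjects per arm with no other TEAE had been lost (pattern C), correction gives (35 + k)/108 and (39 + k)/107:

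| k | Placebo | Dexlansoprazole |
|---|---|---|
| 0 | 32.4% | 36.4% |
| 1 | 33.3% | 37.4% |
| 2 | 34.3% | 38.3% |
| 3 | 35.2% | 39.3% |
| 5 | 37.0% | 41.1% |

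If subjects had instead been counted only through pattern D, correction lowers the figures: for one subject per arm, 34/108 = 31.5% and 38/107 = 35.5%; for three, 32/108 = 29.6% and 36/107 = 33.6%.

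**The case against.** The best reply is that SAP 5.2.3 uses the two protocol terms in their protocol sense. Protocol 10.2.1.2 puts both kinds of event on one eCRF page but omits drug causality and action on study medication for pretreatment events. Protocol 10.1.3 has worsening after first dose recorded as an AE. Each record would then carry an onset-based class that does not need a complete date. On that reading C and D disappear. The reading also respects the purpose of the worst-case step. If every AE that resolved without worsening were pretreatment, the step would protect only unresolved or worsened AEs. This part of the reply stands: the protocol reading is at least as natural as the literal one, although the SAP does not state it.

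Partial dates may also be rare or absent. The protocol asks for start and stop date and time for every event (10.2.1.2), runs logic checks and queries on missing data (12.1), and has visits at Weeks 2 and 4. That stands too.

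It can further be said that worsening on or after Day 1 presupposes an event already present, so the onset condition is implied. That explains the intent, but a date-driven program would not apply a condition that is not written. It also does not help pattern B.

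A reader might infer that the 133 events in Table 8.a are at risk of being lost, since the synopsis says most TEAEs resolved. They are not: they bear on the overlap in pattern A, which leaves the TEAE count unchanged. Table 8.a in fact shows that resolved events were not removed wholesale.

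**Conclusion.** The definition in SAP 5.13.1 conflicts with protocol 10.1.1 and 10.2.1.1. Applied as written, it puts on-treatment AEs that resolve without worsening into the pretreatment listing and SOC/PT summary, and leaves out Screening events that are ongoing and unchanged. This conclusion rests on the text alone.

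The effect on TEAEs is conditional. It requires a partial start date in the month or year of treatment, an imputed start before first dose, and 5.2.3 read through 5.13.1. Given those, a resolved on-treatment AE without worsening could be lost, and an ongoing unchanged Screening event could be added. A reader might conclude that TEAE incidence was understated. The documents do not support that: they show no affected event, give no count of partial dates, and the possible error runs both ways. At about 0.9 points per subject moved, a handful of events would shift the reported incidences modestly. Priority: minor.

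**What to change.** 1. In SAP 5.13.1, define a pretreatment event as an untoward event with onset after informed consent and before the first dose, whatever its end date. Add that worsening on or after Study Day 1 and within 30 days of the last dose counts as a TEAE.
2. In SAP 5.2.3, state that the excluded pretreatment events are those so classed by onset and recorded under the protocol. The worst-case step applies to every other event unless the available date information shows onset before first dose. Tying the exclusion to the recorded class matters: a rule that turned every event with an uncertain start day into an AE could override an investigator-recorded pretreatment event.
3. Confirm which definition was programmed, report the number of partial AE start dates by arm, and rerun the pretreatment and TEAE flags if needed. If there are no such dates, the TEAE counts stand and only the pretreatment text and outputs need checking.

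The cost is a few sentences, one program check and possibly a rerun of the flags. The downside is that pretreatment and TEAE counts may shift slightly, in either direction.
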